9.1. Appendix A Standards for Safety and Immunogenicity Variable Display in TFLs

Continuous Variables

The precision for continuous variables will be based on the precision of the data itself. The mean and median will be presented to one decimal place more than the original results; the SD will be presented to two decimal places more than the original results; the minimum and maximum will be presented to the same precision as the original results. The GMT and corresponding 95% CI will be presented to one decimal place more than the original results. The GMR and corresponding 95% CI will be presented to two decimal places more than the original results. A maximum of three decimal places will be displayed.

Categorical Variables: Percentages and corresponding 95% CI will be presented to 1 decimal place.

9.2. Appendix B Analysis Visit Windows for Safety and Immunogenicity Analysis

Safety and Immunogenicity Analysis will be summarized using the following analysis visit window:

Step 1: If the safety and immunogenicity assessments are collected at scheduled visit, ie, nominal scheduled visit, the data collected at scheduled visit will be used.

Step 2: If the safety and immunogenicity assessments are not collected at the scheduled visit, assessments collected at unscheduled visit will be used using the analysis visit windows described in [Table 1](#) below.

If a subject has multiple assessments within the same analysis visit, the following rule will be used:

- If multiple assessments occur within a given analysis visit, the assessment closest to the target study day will be used.
- If there are 2 or more assessments equal distance to the target study day, the last assessment will be used.

Table 1 Visit Window Mapping Rules

Labs (Hematology, Chemistry, and Coagulation) and Vital Signs		
Visit	Target Study Day	Visit Window in Study Day
Day 1	1 (Date of First Vaccination)	≤ 1 Pre-dose
Day 1, 1-hour post dose (if Vital Signs)	1	1-hour Post-dose
Day 8	8	[1 Post-dose, 18], if Labs; [After 1 Hour Post-dose, 18], if Vital Signs
Month 1	29	[19, 42]
Month 2	56 (Date of Second Vaccination)	[43, 59]
Day 63	63	[60, 73]
Month 3	84	[74, 125]
Month 6	168 (Date of Third Vaccination)	[126, 171]
Day 175	175	[172, 185]
Month 7	196	[186, 265]
Month 12 (Vital Signs Only)	336	[266, 419]
Antibody-Mediated Immunogenicity		
Visit	Target Study Day	Visit Window
Subjects completing all vaccinations and subjects completing first and third vaccinations only		
Day 1	1 (Date of First Vaccination)	≤1 Pre-dose
Month 1	29	[1 Post-dose, 42]
Month 2	56 (Date of Second Vaccination)	[43, 70] Pre-second-dose
Month 3	84	[70 Post-second-dose, 125]
Month 6	168 (Date of Third Vaccination)	[126, 182] Pre-third-dose
Month 7	196	[182 Post-third-dose, 265]
Month 12	336	[266, 419]

Month 18	504	≥ 420
Subjects completing the first 2 vaccination only		
Day 1	1 (Date of First Vaccination)	≤ 1 Pre-dose
Month 1	29	[1 Post-dose, 42]
Month 2	56 (Date of Second Vaccination)	[43, 70] Pre-second-dose
Month 3	84	[70 Post-second-dose, 167]
Month 8	252	[168, 335]
Month 14	420	≥ 336
Subjects completing the first vaccination only		
Day 1	1 (Date of First Vaccination)	≤ 1 Pre-dose
Month 1	29	[1 Post-dose, 98]
Month 6	168	[99, 251]
Month 12	336	≥ 252
CMI		
Visit	Target Study Day	Visit Window
Subjects completing all vaccinations and subjects completing first and third vaccinations only		
Day 1	1 (Date of First Vaccination)	≤ 1 Pre-dose
Day 8	8	[1 Post-dose, 31]
Month 2	56 (Date of Second Vaccination)	[32, 59] Pre-second-dose
Day 63	63	[59 Post-second-dose, 115]
Month 6	168 (Date of Third Vaccination)	[116, 171] Pre-third-dose
Day 175	175	[171 Post-third-dose, 255]
Month 12	336	[256, 419]

Month 18	504	≥ 420
Subjects completing the first 2 vaccination only		
Day 1	1 (Date of First Vaccination)	≤ 1 Pre-dose
Day 8	8	[1 Post-dose, 31]
Month 2	56 (Date of Second Vaccination)	[32, 59] Pre-second-dose
Day 63	63	[59 Post-second-dose, 157]
Month 8	252	[158, 335]
Month 14	420	≥ 336
Subjects completing the first vaccination only		
Day 1	1 (Date of First Vaccination)	≤ 1 Pre-dose
Day 8	8	[1 Post-dose, 87]
Month 6	168	[88, 251]
Month 12	336	≥ 252

9.3. Appendix C Imputation Rules for Missing Prior/Concomitant Medications and Non-Study Vaccinations

Imputation rules for missing or partial medication start/stop dates are defined below:

1. Missing or partial medication start date:
 - a. If only DAY is missing, use the first day of the month.
 - b. If DAY and Month are both missing, use the first day of the year.
 - c. If DAY, Month and Year are all missing, the date will not be imputed, but the medication will be treated as though it began prior to the first vaccination for purposes of determining if status is prior or concomitant.
2. Missing or partial medication stop date:

- a. If only DAY is missing, use the earliest date of (last day of the month, study completion, discontinuation from the study, or death).
- b. If DAY and Month are both missing, use the earliest date of (last day of the year, study completion, discontinuation from the study, or death).
- c. If DAY, Month and Year are all missing, the date will not be imputed, but the medication will be flagged as a continuing medication.

In summary, the prior, concomitant or post categorization of a medication is described in [Table 2](#) below.

Table 2 Prior, Concomitant, and Post Categorization of a Medication

Medication Start Date	Medication Stop Date		
	< First Dose Date of Study Vaccination	≥ First Dose Date and ≤ 28 Days After Last Vaccination [3]	> 28 Days After Last Vaccination [2]
< First dose date of study vaccination [1]	P	PC	PCA
≥ First dose date and ≤ 28 days after last vaccination	-	C	CA
> 28 days after last vaccination	-	-	A

A: Post; C: Concomitant; P: Prior

[1] includes medications with completely missing start date

[2] includes medications with completely missing end date

[3] calculated as Date of Last Study Vaccination + 27 days

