Recording of SAEs and concomitant medications relevant to or for the treatment of the SAE 	X	X	X	X	X	X	X	X	X	X	X	X	X	X
Study completion 														X

Abbreviations: AE = adverse event; AR = adverse reaction; C = clinic visit; COVID-19 = coronavirus disease-2019; D = day; eDiary = electronic diary; EUA = Emergency Use Authorization; FDA = US Food and Drug Administration; ICF = informed consent form; M = month; MAAE = medically-attended adverse event; SAE = serious adverse event; SC = safety (phone) call; SN = seronegative participants; SP = seropositive participants.

-  Please refer to [Section 7.1](#), [Table 6](#) and [Table 7 \(Appendix 2\)](#) for participants not completing all vaccinations.
-  Based on prior approval from the Sponsor, the Screening visit may be performed across 2 separate clinic visits. In Part 1, screening may occur up to 28 days prior to Visit Day 1. In Part 2, the screening window is 28 days (Days -27 to 0) for CMV-seronegative participants and 42 days (Days -41 to 0) for CMV-seropositive participants.
-  Physical examination: a full physical examination, including height and weight, will be performed at Screening; symptom-directed physical examinations will be performed at all other scheduled timepoints. Interim physical examinations will be performed at the discretion of the Investigator. Any clinically significant finding identified during a study visit should be reported as a MAAE.
-  Vital signs to be collected pre and post-dosing on days of vaccination (Day 1, Day 56, and Day 168).
-  Pregnancy test at Screening will be included in blood testing; pregnancy testing before each study vaccination (or at any time at the discretion of the Investigator) will be a point-of-care urine test.
-  Screening laboratory tests:
  - CMV IgG with reflex to IgM
  - Serology: HBsAg, hepatitis C virus antibody, HIV type 1 and 2 antibodies
  - Hematology: hemoglobin, platelet count, and total and differential white blood cell count
  - Chemistry: alanine aminotransferase (ALT), alkaline phosphatase (ALP), aspartate aminotransferase (AST), total bilirubin, creatinine, random glucose
  - Coagulation: PTT and PT
  - FSH level may be measured to confirm menopausal status at the discretion of the Investigator.
-  Safety laboratory tests:

- Hematology: hemoglobin, platelet count, total and differential white blood cell count

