### **8.5. Physical Examination and Vital Signs**

A full physical examination will be performed during the screening period according to standard medical practice, including assessment of vital signs, height, and weight. Vital sign measurements include the assessment of body temperature, systolic and diastolic blood pressures, heart rate, and respiratory rate. The information collected will be recorded in the eCRF.

On days of dosing, vital signs will be collected prior to dosing and approximately 60 minutes after dosing, prior to discharge of the participant.

Symptom-directed physical examinations will be performed at all other scheduled timepoints. Interim physical examinations will be performed at the discretion of the Investigator.

Treatment of any abnormality observed during physical examination should be performed according to local medical practice outside the study or by referral to an appropriate healthcare provider at the discretion of the Investigator.

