6.3.4. Vital Sign Measurements

Vital sign measurements, including systolic and diastolic blood pressures, heart rate, respiratory rate, and body temperature, will be presented in a data listing. The values meeting the toxicity grading criteria will be flagged in the data listing. The abnormalities meeting the toxicity grading criteria (Grade 2 or higher) in any vital sign measurement will be listed separately. If a subject has a vital sign result with Grade 2 or higher abnormality at any post vaccination visit, then all results of vital sign measurement for that subject will be presented in the listing.

Observed values and changes from baseline for all vital sign measurements will be summarized at each scheduled visit by CMV serostatus (CMV-seropositive, CMV-seronegative, and overall) and vaccination group as defined in [Section 6.1](#). Shift from baseline in the toxicity grades will also be summarized at each scheduled visit by CMV serostatus and vaccination group.

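### As written, the SAP's tie rule would report the 1-hour post-dose vital signs as the ordinary Month 2 and Month 6 values

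*SAP*

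**What the plan says.** Protocol Section 1.3, Table 1, footnote 4 sets the schedule: "Vital signs to be collected pre and post-dosing on days of vaccination (Day 1, Day 56, and Day 168". Protocol Section 8.5 gives the timing: "On days of dosing, vital signs will be collected prior to dosing and approximately 60 minutes after dosing, prior to discharge of the participant". Each dosing visit therefore yields two planned readings on one calendar date.

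SAP Section 6.3.4 sets the output: "Observed values and changes from baseline for all vital sign measurements will be summarized at each scheduled visit". Shifts in toxicity grade are also tabulated by scheduled visit. The section has no rule for pre-dose and post-dose timepoints.

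SAP Appendix B maps readings to visits. Step 1 uses data from the nominal scheduled visit. Step 2 uses the Table 1 windows for unscheduled data when the scheduled assessment is missing. If an analysis visit holds several assessments, the one nearest the target day is taken, and then: "If there are 2 or more assessments equal distance to the target study day, the last assessment will be used".

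In the labs and vital signs block of Table 1, Day 1 has a pre-dose row and a separate row labelled "Day 1, 1-hour post dose (if Vital Signs". The Day 8 row starts, for vital signs, after the 1-hour reading. Month 2 (target 56, window [43, 59]) and Month 6 (target 168, window [126, 171]) have no such split. The antibody and CMI blocks restrict the same two visits to samples taken before the dose.

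**The concern.** The combined block suits laboratory tests, which are drawn only before dosing on vaccination days (Protocol Section 8.8.2). It does not suit vital signs, which are also taken after the dose. The treatment of Day 1 and Day 8 shows that the 1-hour reading was considered for Dose 1, so its absence for Doses 2 and 3 looks like an omission.

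Baseline is the last value before the first dose (SAP Section 6.1). If the post-dose reading is kept, the Month 2 and Month 6 changes from baseline are changes to one hour after an injection. They would carry an ordinary visit label and stand beside non-dosing visits such as Day 8, Month 1, Month 3 and Month 7. The by-visit tables would show pre-dose and post-dose values separately for Dose 1 but not for Doses 2 and 3. An abnormality seen before Dose 2 or Dose 3 and gone an hour later would be missing from that visit's shift. SAP Section 6.3.3 tabulates laboratory shifts to the worst post-baseline result, but vital-sign shifts are by visit.

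**Working it through.** The plan gives no figure to reproduce, so the check is to apply the written rule.

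**Inputs**
- Two readings per dosing visit, pre-dose and about 60 minutes post-dose (Protocol Section 1.3, Table 1, footnote 4; Section 8.5).
- Study day = assessment date − first vaccination date + 1 (SAP Section 6.1). It uses dates, not clock times. SAP Section 6.1 also defines a study day relative to the most recent vaccination, which does use time of day. The Table 1 targets run on through 56, 168 and 336, so they are counted from the first dose.
- Targets: 56 for Month 2, 168 for Month 6 (SAP Appendix B, Table 1).
- Selection: smallest distance |study day − target|, then the last assessment on a tie (SAP Appendix B).

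**Applying it**

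| Visit | Study day of dose | Distance, pre-dose | Distance, post-dose | Selected |
|---|---|---|---|---|
| Month 2 | 49 | 7 | 7 | post-dose |
| Month 2 | 56 | 0 | 0 | post-dose |
| Month 2 | 57 | 1 | 1 | post-dose |
| Month 2 | 63 | 7 | 7 | post-dose |
| Month 2 | 112 | 56 | 56 | post-dose |
| Month 6 | 161 | 7 | 7 | post-dose |
| Month 6 | 168 | 0 | 0 | post-dose |
| Month 6 | 175 | 7 | 7 | post-dose |

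All eight cases tie, and all eight give the post-dose reading. Days 63, 112 and 175 lie outside the Table 1 windows and reach Month 2 or Month 6 through Step 1; the tie is the same.

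**Count.** Planned dosing-day readings: 3 visits × 2 = 6. Readings kept in the by-visit tables: 2 (Day 1) + 1 (Month 2) + 1 (Month 6) = 4. So 2 of 6 drop out for a participant who receives all three doses. A participant with only the first two doses is affected at Month 2 only, and one with only the first dose not at all.

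**The case against.** **Step 1 may settle it.** Both readings are scheduled, so Step 1 covers them and the windows, which serve unscheduled data, may never apply. If the eCRF records pre-dose and post-dose as separate timepoints, programmers could report both. That is possible; the eCRF and table shells are not in the documents. But Step 1 does not choose between two scheduled readings on one date, and the SAP names no post-dose analysis visit for Month 2 or Month 6. The multiple-assessment rule is the only selector written down, so the conclusion stands as a statement about the rule, not about what programmers will do.

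**Little depends on it.** This stands. A reader might infer that the pre-dose readings are lost, or that the acute change after Doses 2 and 3 cannot be seen anywhere. The documents do not support that. SAP Section 6.3.4 lists all vital signs, flags graded values, and lists every vital-sign result for a participant with a Grade 2 or higher value after vaccination. Protocol Section 8.9.2 has Grade 3 or higher vital signs entered as adverse events.

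A reader might also infer bias between vaccine and placebo. Both arms have the same schedule and the same rule, so they are compared at the same timepoint. The retained reading is the post-injection one, so the tables would not hide an acute abnormality present at one hour.

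Nor is this a contrast between resting and non-resting values: Protocol Appendix 3, Table 8 asks for rest at every vital-sign measurement. The contrast is before against after injection.

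**Conclusion.** The concern holds as a labelling fault in a stated rule. Taken literally, the rule makes the 1-hour post-dose reading the Month 2 and Month 6 value in the by-visit summaries, changes from baseline and grade shifts. It affects two of the three dosing visits, all five vital signs (systolic and diastolic pressure, heart rate, respiratory rate, temperature) and both serostatus groups, for anyone who receives the dose in question and has both readings.

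The severity is low. Vital signs are not among the primary, secondary or exploratory endpoints, the study tests no hypothesis, and laboratory summaries are untouched. The documents give no vital-sign data, so the effect on any tabulated value cannot be estimated.

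The conclusion assumes that both readings are assigned to the single analysis visit named in Table 1 and that no shell or programming specification outside these documents overrides the tie rule.

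**What to change.** Change SAP Appendix B, Table 1 for vital signs only, splitting them from the labs rows, which stay as they are:

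| Vital-signs row | Window |
|---|---|
| Month 2 | [43, 59] Pre-second-dose |
| Month 2, 1-hour post dose | 1 hour after second dose |
| Day 63 | After 1 hour post-second-dose, to 73 |
| Month 6 | [126, 171] Pre-third-dose |
| Month 6, 1-hour post dose | 1 hour after third dose |
| Day 175 | After 1 hour post-third-dose, to 185 |

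Apply the nearest-then-last rule within each row.

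The Day 63 and Day 175 changes are needed because those rows now start at 60 and 172. With doses on Days 56 and 168, an unscheduled reading more than an hour after the dose, up to Day 59 or Day 171, would otherwise fall in no row. The Day 8 row already avoids this gap after Dose 1. The SAP should also say where an unscheduled reading goes when the dose is late (after Day 59 or Day 171) or is not given.

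The protocol already schedules every reading, so no new data are needed. SAP version 5.0 was written to update the analyses before final database lock, which makes it the natural place for the change. The cost is two extra rows, some programming and slightly longer output. If the interim vital-signs tables used the undivided rows, a footnote should explain why the final Month 2 and Month 6 values differ.

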-  All scheduled study visits should be completed within the defined visit window. Timing of Dose 3 is calculated in relation to Dose 1 (Day 1) and should not shift later than 167 days ( $\pm 7$  days) after Day 1; succeeding follow-up visits (Visits 10-17) are scheduled in relation to Dose 3. In the event the participant is not able to come on site for a clinic visit as a result of the COVID-19 pandemic (self-quarantine or disruption of clinical site activities following business continuity plans and/or local government mandates for “stay at home” or “shelter in place”), a safety call to the participant should be made in place of the clinic visit. The safety call should encompass all scheduled visit assessments that can be completed remotely, such as assessment for AEs and concomitant medications (eg, as defined in scheduled safety calls at Visits 12-15). Home visits will be permitted for all non-dosing visits in the event a participant cannot make it to the clinic as a result of the COVID-19 pandemic. Home visits must be permitted by the site IRB and the participant via informed consent and have prior approval from the Sponsor (or its designee).

-  In the event the visit for Dose 2 is disrupted and cannot be completed at Day 56  $\pm$  7 days as a result of the COVID-19 pandemic (COVID-19 vaccination under the FDA EUA or FDA approval, self-quarantine or disruption of clinical site activities following business continuity plans and/or local government mandates for “stay at home” or “shelter in place”), the window may be extended to Day 56 + 56 days (i.e., to 4 -months). When the extended window is utilized, the Day 84 visit is to be completed at 28 (-7 to +21) days after Dose 2 and monthly safety calls should occur every 28 days  $\pm$  7 days until the Month 6 visit (Day 168) for Dose 3. Dose 3 timing should continue to be based on Dose 1 and should not be adjusted if Dose 2 occurs in the extended dosing window (Dose 3 should not shift later than 167 days [ $\pm$  7 days] after Day 1); succeeding follow-up visits (Visits 10-17) are scheduled in relation to Dose 3.
-  Only documentation of COVID-19 vaccine is required.
-  Upon completion of final study procedures, including the final assessment and recording of MAAEs and SAEs, the participant’s treatment assignment may be unblinded via the IRT system.

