6.1. General Considerations

The Schedule of Assessments is provided in the protocol Table 1 for subjects completing all vaccinations, Table 6 for subjects completing the first 2 vaccinations only, and Table 7 for subjects who completing the first vaccination only.

Continuous variables will be summarized using the following descriptive summary statistics: the number of subjects (n), mean, standard deviation (SD), median, minimum (min), and maximum (max).

Categorical variables will be summarized using counts and percentages.

Baseline value, unless specified otherwise, will be defined as the most recent non-missing measurement (scheduled or unscheduled) collected before the first dose of study vaccination.

For the summary statistics of all numerical variables unless otherwise specified, the display precision will follow programming standards. Please see [Appendix A](#) for variable display standards.

When count data are presented, the percentage will be suppressed when the count is zero in order to draw attention to the non-zero counts. A row denoted “Missing” will be included in count tabulations where specified on the shells to account for dropouts and missing values. The denominator for all percentages will be the number of subjects in that vaccination group within the analysis set of interest, unless otherwise specified.

Study day relative to the first vaccination will be calculated as below:

- a) study day prior to the first vaccination will be calculated as: date of assessment/event – date of the first vaccination;
- b) study day on or after the date of the first vaccination will be calculated as: date of assessment/event – date of the first vaccination + 1;

Study day relative to the most recent vaccination will be calculated as below:

- a) study day prior to the first vaccination will be calculated as: date of assessment/event – date of the first vaccination;
- b) study day on or after the date of the first vaccination but before the second vaccination (if applicable) will be calculated as: date of assessment/event – date of the first vaccination + 1;

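### Analysis visit windows count from Day 1 and do not follow a delayed Dose 2, so unscheduled replacement results can get the wrong visit label and, for labs and vital signs, the wrong side of a dose

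*SAP*

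**What the plan says.** SAP Appendix B assigns results to visits in two steps. Under Step 1, where a nominal visit took place, "the data collected at scheduled visit will be used". Under Step 2, if the scheduled assessment was not collected, an unscheduled one is placed by the windows in Table 1.

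For participants with all three doses, or with the first and third only, the antibody rows are:
- Month 2: Days 43-70, before Dose 2.
- Month 3: "70 Post-second-dose, 125".
- Month 6: "126, 182] Pre-third-dose".

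The lab and vital-sign rows are Month 2 (43-59), Day 63 (60-73), Month 3 (74-125), Month 6 (126-171) and Day 175 (172-185). None of these carries a pre- or post-dose qualifier.

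Protocol Table 1, footnote 14, covers a Dose 2 disrupted by COVID-19: "the window may be extended to Day 56 + 56 days". In that case "the Day 84 visit is to be completed at 28 (-7 to +21) days after Dose 2", while "Dose 3 timing should continue to be based on Dose 1".

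SAP 6.1 defines two day counts. One runs from the first vaccination: "study day on or after the date of the first vaccination will be calculated as" the date difference plus 1. The other follows the latest dose: "Study day relative to the most recent vaccination will be calculated as below". Appendix B does not say which it uses, but its targets (56, 84, 168) fit only the first.

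**The concern.** The protocol ties the one-month post-Dose-2 sample to the actual Dose 2 date, whereas the SAP windows assume that Dose 2 was given on Day 56. When the two differ, Step 2 can give the wrong visit label to a replacement result that was drawn on time.

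GMTs and GMRs of neutralizing antibody at each timepoint are primary endpoints, and Month 3 is also an ANCOVA timepoint in SAP 6.4.2. Lab and vital-sign values and changes from baseline are summarized by visit, as are the vital-sign toxicity-grade shifts, so a pre-dose result could be reported under a post-dose visit or the reverse. Pandemic disruption can both delay Dose 2 and cause clinic visits to be missed, so the two conditions may coincide in the same participants.

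**Working it through.** **1. How the windows were built.** Each boundary is the midpoint of adjacent targets counted from Day 1. Month 2/Month 3: (56 + 84)/2 = 70. Month 3/Month 6: (84 + 168)/2 = 126, so Month 3 ends on Day 125. All 32 boundaries in the lab/vital-sign, antibody and cell-mediated blocks reproduce in this way. The table therefore assumes Dose 2 on Day 56.

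**2. Month 3 antibody replacement after a late Dose 2.** The latest Dose 2 is Day 56 + 56 = 112. The visit is due at +21 to +49 days, target +28: Days 133 to 161, target 140. All of these days lie in the Month 6 window (126-182, before Dose 3).
- For the latest allowed sample this starts with Dose 2 on Day 77 (77 + 49 = 126).
- For the 28-day target it starts with Dose 2 on Day 98 (98 + 28 = 126).
- The sample is after Dose 2 and before Dose 3, so the side of each dose is right and only the visit is wrong.
- It is lost from Month 3. It enters Month 6 only if the scheduled Month 6 sample is also missing, because Step 1 takes precedence.
- Participants with only the first two doses have a Month 3 window running to Day 167, which contains Days 133-161, so they are unaffected for this sample.

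**3. Pre-Dose-2 antibody replacement, Days 71-112.** This misses Month 2, which ends on Day 70. If the post-second-dose qualifier in the Month 3 row applies only to the Day 70 bound, the sample is labelled Month 3, and is used there if no scheduled Month 3 sample exists. If the qualifier applies to the whole window, the sample has no window. The Month 1 row, which runs from Day 1 post-dose to Day 42, uses the same notation and favors the first reading without settling it.

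**4. Labs and vital signs.**
- Delayed Dose 2: pre-dose results on Days 60-73 map to Day 63 and those on Days 74-112 map to Month 3. Both are post-Dose-2 visits.
- Ordinary timing (±7 days), Dose 2 on Days 49-52: a result 7 days later falls on Days 56-59, which is Month 2.
- Ordinary timing, Dose 3 on Days 161-164: a result 7 days later falls on Days 168-171, which is Month 6. Month 2 and Month 6 are the dosing visits, at which the protocol requires blood to be drawn before vaccination.

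**5. Size for one misassigned titer.** The factor on the GMT is r^(1/n), where r is the fold difference. The documents give no titer kinetics, so r = 2 to 3 is an assumption.

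| Vaccine group | n | r = 2 | r = 3 |
|---|---|---|---|
| Part 1 seropositive, 24 × 3/4 | 18 | 1.039 | 1.063 |
| Part 1 seronegative, 60 × 3/4 | 45 | 1.016 | 1.025 |
| Selected dose, seronegative, 45 + 80 × 3/4 | 105 | 1.007 | 1.011 |
| Selected dose, seropositive, 18 + 120 × 3/4 | 108 | 1.006 | 1.010 |

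The last two rows apply to the final analysis, which SAP 6.5 says combines Parts 1 and 2.

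**The case against.** The strongest defense is Step 1. The Day 84 visit that moves with Dose 2 is still a scheduled visit, so a delayed participant who attends keeps the correct label on any calendar day. The windows act only when the scheduled result is missing and an unscheduled one exists. The protocol plans no replacement antibody draws: visits missed through the pandemic become safety calls or home visits, and the extra collections allowed under protocol Table 2 are for following up abnormal results. For a late Month 3 sample to reach Month 6, the scheduled pre-Dose-3 sample must be missing as well, in someone who did receive Dose 3. All of this stands, and it keeps the effect small.

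The lab consequences are also limited. Baseline precedes Dose 1, and the lab toxicity shift uses the worst post-baseline grade, so neither depends on these labels. By-visit lab summaries and the by-visit vital-sign summaries and shifts still do.

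The sensitivity analysis for widened windows in SAP 6.4.4 does not remove the problem. It is optional, concerns Part 1 only, and excludes data without correcting labels.

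A reader might infer that delayed participants' antibody samples are generally put on the wrong side of a dose. The documents do not support that: the Day 133-161 sample is on the right side of both doses, and the pre-Dose-2 case depends on an ambiguous qualifier.

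**Conclusion.** The Step 2 windows conflict with the protocol's own schedule for a late Dose 2 and are wrong as written. For antibodies, the certain error is a wrong visit, with loss from Month 3; an error about the side of Dose 2 arises on only one reading of the qualifier. For labs and vital signs, a result can be put on the wrong side of a dose without ambiguity, with or without a pandemic delay.

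This is a minor point. The number of affected results is not given and is probably small. A reader might take the 4-6% shift as the expected effect on the primary endpoint. It is not: it is the effect of one sample in the smallest vaccine arm under an assumed 2- to 3-fold difference. The same sample moves the GMT by about 1.6-2.5% in an arm of 45 and about 0.6-1.1% in the pooled selected-dose groups.

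**What to change.** In Step 2 of SAP Appendix B:
- Map unscheduled results by actual dose dates and times, using the day count relative to the most recent vaccination that SAP 6.1 already derives, bounded by the next actual dose.
- Add pre/post-dose qualifiers to the lab and vital-sign rows at Doses 2 and 3.
- State that the post-second-dose and post-third-dose qualifiers apply to the whole window.
- For participants with the first and third doses only, keep the Day 1 windows up to the actual third dose.
- Add a tie rule between Month 3 and Month 6 for a late Dose 2. With Dose 2 on Day 112 the re-anchored midpoint is (140 + 168)/2 = 154, but the Month 3 visit may run to Day 161, so Days 154-161 are contested. One option is to assign samples 21-49 days after Dose 2 to Month 3 unless Month 3 is already filled. Because the SAP count adds 1, these are relative study days 22-50.

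The cost is a small change to the derivation code and one extra rule. SAP version 5.0 was written before final database lock, and the variable needed already exists.
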